5 SUPPORTIVE CARE

For both the administration of PSA-TRICOM and enzalutamide, antiemetics, stool softeners and antidiarrheal agents may be administered as required, but are not anticipated to be needed and should not be used prophylactically on the first cycle. The selection of the specific antiemetic regimen is at the discretion of the treating physician. Antiemetic regimens will not include steroids.

Other supportive care with blood components, antibiotics, analgesics, general medical therapy, etc., will be delivered as required. Any patients taking antibiotics for any reason must complete that course of therapy and be free of evidence of further infection before receiving any dose of vaccine.

Symptomatic anemia should be treated with appropriate red blood cell or erythropoietin support. Thrombocytopenia should be treated conservatively. In the absence of bleeding or a planned invasive procedure, platelet transfusions should be given for a platelet count below 10,000/mm³. If invasive procedures are planned or the patient develops bleeding, platelet transfusions should be administered in accordance with the standard of practice, usually maintaining a platelet count of > 50,000/mm³.

Any evidence of disseminated intravascular coagulation (DIC), hemolytic uremic syndrome (HUS), or thrombotic thrombocytopenic purpura (TTP) including thrombocytopenia, hemolytic anemia, renal failure, fever or neurologic changes should be thoroughly evaluated and closely monitored and supported as clinically indicated.

5.1 EXCLUDED MEDICATIONS

While patients on protocol treatment, all medications required for the health of the patient are allowed with the following exceptions:

- Concurrent chemotherapy
- Concurrent radiation therapy
- Concurrent immunotherapy
- Concurrent anti-cancer radionuclides
- Concurrent systemic corticosteroid use (daily or every other day for continued use > **14 days**; See section **2.1.2**)
- Concomitant use of secondary hormonal treatments

5.2 TREATMENT OF VACCINIA VACCINATION COMPLICATION

5.2.1 Vaccinia Immune Globulin:

First-line treatment of some of the complications of vaccinia caused by dissemination of vaccinia virus (severe cases of inadvertent inoculation involving extensive lesions or if comorbid conditions exist, severe cases of generalized vaccinia in patients that are systemically ill and whose condition might be toxic or who have serious underlying immunosuppressive illnesses, eczema vaccinatum, and progressive vaccinia) is with VIG.

VIG is contraindicated, however, for the treatment of isolated vaccinia keratitis. VIG is a sterile solution of the immunoglobulin fraction of pooled plasma from individuals inoculated with vaccinia vaccine. VIG is an investigational agent available through the CDC's Strategic National Pharmaceutical Stockpile under an IND protocol by contacting the CDC's Smallpox Vaccine Adverse Events Clinician Information Line at [name]. Upon receipt of a call from a patient or upon direct observation of a patient or contact who manifests signs and symptoms of any of the above conditions, the investigator should place a call to the CDC as soon as possible:

- 1) to initiate review of the clinical case,
- 2) to seek consultation on the appropriateness of VIG therapy,
- 3) to determine the appropriate VIG dose and dosing method for administration, if VIG therapy is required, and
- 4) to determine how to access and have the appropriate doses of VIG delivered.

Early institution of VIG therapy is advised following recognition of clinical symptoms compatible with some vaccinia complications (eczema vaccinatum, severe generalized vaccinia, progressive vaccinia, and some cases of inadvertent inoculation). The effectiveness of VIG therapy appears to be time dependent. VIG has not proven to be of benefit in the treatment of post-vaccinia encephalitis, and is contraindicated for treatment of isolated vaccinia keratitis due to the increased risk of corneal scarring.

A new intravenous formulation of VIG is available through the CDC, which has a lower level of aggregated protein, allowing it to be used by either the IM or IV route. This formulation will most likely be preferred for administration and investigators will be instructed by the CDC regarding appropriate dosing and method of administration based on formulation and availability. There is no guarantee that VIG will successfully treat complications. At present, there are no other anti-viral therapies of proven benefit for the treatment of vaccinia-related complications.

5.2.2 Cidofovir (Vistide®, Gilead Sciences):

Cidofovir is an FDA-approved antiviral drug for the treatment of CMV retinitis among patients with AIDS. Cell-based in vitro studies and animal model studies have demonstrated antiviral activity of this agent against certain orthopoxviruses. Currently, efficacy in the treatment of vaccinia-related complications in humans is unknown. According to the CDC, “VIG is recommended as first line of therapy. Cidofovir may be considered as a secondary treatment, and will only be released by the CDC after all inventories of VIG have been exhausted, after a patient fails to improve with VIG treatment, or as a last effort for a patient who is otherwise near death.” [Medical Management of Smallpox (Vaccinia) Vaccine Adverse Reactions: Vaccinia Immune Globulin and Cidofovir. Last updated February 11, 2003. Available at: <http://www.bt.cdc.gov/agent/smallpox/vaccination/mgmt-adv-reactions.asp>].

6 DATA COLLECTION AND EVALUATION

6.1 DATA COLLECTION

The PI will be responsible for overseeing entry of data into an in-house password protected electronic system and ensuring data accuracy, consistency and timeliness. The principal investigator, associate investigators/research nurses and/or a contracted data manager will assist with the data management efforts. All data obtained during the conduct of the protocol will be kept in secure network drives or in approved alternative sites that comply with NIH security standards. Primary and final analyzed data will have identifiers so that research data can be attributed to an individual human subject participant.

- 6.1.1 Eligible patients must be confirmed and checklist completed. Consent form must be signed prior to registration with Central Registration Information Services.
- 6.1.2 Data will be secured in NCI C3D database. Data will be collected using protocol-specific case report forms, and verified for accuracy and completeness. Hard copies of data will be stored in locked secured areas and data will be entered onto a secured electronic data base. The following protocol-specific study forms will be complete and stored: eligibility checklist (developed by Central Registration Office, CRO). A copy of all serious AE forms will be kept in the research record.
- 6.1.3 Treatment is given according to protocol (dated notes about doses given, complications, and clinical outcomes).
- 6.1.4 Toxicity is assessed according to protocol (laboratory report slips, etc.)
- 6.1.5 Response is assessed according to protocol (X-ray, scan, lab reports, and date noted on clinical assessment, as appropriate).
- 6.1.6 Drug Accountability Records are kept for each patient.
- 6.1.7 We will not report Grade 1 adverse events.

All adverse events, including clinically significant abnormal findings on laboratory evaluations, regardless of severity, will be followed until return to baseline or stabilization of event. Patients will be followed for adverse events for a minimum of 30 days after removal from study treatment or until off-study, whichever comes first.

An abnormal laboratory value will be recorded in the database as an AE **only** if the laboratory abnormality is characterized by any of the following:

- Results in discontinuation from the study
- Is associated with clinical signs or symptoms
- Requires treatment or any other therapeutic intervention
- Is associated with death or another serious adverse event, including hospitalization.
- Is judged by the Investigator to be of significant clinical impact
- If any abnormal laboratory result is considered clinically significant, the investigator will provide details about the action taken with respect to the test drug and about the patient's outcome.

End of study procedures: Data will be stored according to HHS, FDA regulations and NIH Intramural Records Retention Schedule as applicable.

Loss or destruction of data: Should we become aware that a major breach in our plan to protect subject confidentiality and trial data has occurred, the IRB will be notified.

6.2 RESPONSE CRITERIA

Patients will not undergo scheduled radiographic assessment for metastatic disease unless clinically indicated for increasing PSA or symptoms.

6.2.1 Disease Progression

6.2.1.1 PSA will not be used to measure progression of disease given the intermittent use of enzalutamide. It is expected that PSA will rise after a 3 month course of enzalutamide is completed and the treatment is discontinued. Patients will be offered androgen deprivation therapy (ADT) as clinically indicated or a second course of enzalutamide as indicated in the protocol. Starting ADT will be done at the discretion of the investigator, although this will result in treatment termination and removal from the clinical trial. (Conventionally this is when PSA has a doubling time of less than 3 months, but patients may refuse treatment in favor of surveillance which is also clinically appropriate. Conversely, patients may go on ADT at any time, although this

may result in removal from the trial.) PSA will be used to calculate PSA kinetics/tumor growth kinetics.

6.2.1.2 Development of a new bone lesion.

6.2.1.3 Development of a soft tissue mass, identified on CT scan or physical exam, consistent with metastatic prostate cancer. If identified on physical exam, the lesion may be biopsied to confirm the presence of prostate cancer.

6.2.1.4 Development of urethral, ureteral, or spinal cord obstruction secondary to tumor.

6.2.1.5 Development of cytologically positive pleural effusion or lymphangitic spread in the lungs.

6.2.1.6 Symptoms which in the opinion of the investigator are consistent with clinical progression.

6.3 TOXICITY CRITERIA

The following adverse event management guidelines are intended to ensure the safety of each patient while on the study. The descriptions and grading scales found in the revised NCI Common Terminology Criteria for Adverse Events (CTCAE) version 4.0 will be utilized for AE reporting. All appropriate treatment areas should have access to a copy of the CTCAE version 4.0. A copy of the CTCAE version 4.0 can be downloaded from the CTEP web site (http://ctep.cancer.gov/protocolDevelopment/electronic_applications/ctc.htm#ctc_40).

7 SAFETY REPORTING REQUIREMENTS/DATA AND SAFETY MONITORING PLAN

7.1 DEFINITIONS

7.1.1 Adverse Event

Any untoward medical occurrence in a human subject, including any abnormal sign (for example, abnormal physical exam or laboratory finding), symptom, or disease, temporally associated with the subject's participation in research, whether or not considered related to the subject's participation in the research.

7.1.2 Suspected adverse reaction

Suspected adverse reaction means any adverse event for which there is a reasonable possibility that the drug caused the adverse event. For the purposes of IND safety reporting, 'reasonable possibility' means there is evidence to suggest a causal relationship between the drug and the adverse event. A suspected adverse reaction implies a lesser degree of certainty about causality than adverse reaction, which means any adverse event caused by a drug.

7.1.3 Unexpected adverse reaction

An adverse event or suspected adverse reaction is considered "unexpected" if it is not listed in the investigator brochure or is not listed at the specificity or severity that has been observed; or, if an investigator brochure is not required or available, is not consistent with the risk information described in the general investigational plan or elsewhere in the current application.

"Unexpected", also refers to adverse events or suspected adverse reactions that are mentioned in the investigator brochure as occurring with a class of drugs or as anticipated from the pharmacological properties of the drug, but are not specifically mentioned as occurring with the particular drug under investigation.

7.1.4 Serious

An Unanticipated Problem or Protocol Deviation is serious if it meets the definition of a Serious Adverse Event or if it compromises the safety, welfare or rights of subjects or others.

7.1.5 Serious Adverse Event

An adverse event or suspected adverse reaction is considered serious if in the view of the investigator or the sponsor, it results in any of the following:

- Death,
- A life-threatening adverse drug experience
- Inpatient hospitalization or prolongation of existing hospitalization
- Persistent or significant incapacity or substantial disruption of the ability to conduct normal life functions
- A congenital anomaly/birth defect.
- Important medical events that may not result in death, be life-threatening, or require hospitalization may be considered a serious adverse drug experience when, based upon appropriate medical judgment, they may jeopardize the patient or subject and may require medical or surgical intervention to prevent one of the outcomes listed in this definition.

7.1.6 Disability

A substantial disruption of a person's ability to conduct normal life functions.

7.1.7 Life-threatening adverse drug experience

Any adverse event or suspected adverse reaction that places the patient or subject, in the view of the investigator or sponsor, at immediate risk of death from the reaction as it occurred, i.e., it does not include a reaction that had it occurred in a more severe form, might have caused death.

7.1.8 Protocol Deviation (NIH Definition)

Any change, divergence, or departure from the IRB-approved research protocol.

7.1.9 Non-compliance (NIH Definition)

The failure to comply with applicable NIH Human Research Protections Program (HRPP) policies, IRB requirements, or regulatory requirements for the protection of human research subjects.

7.1.10 Unanticipated Problem

Any incident, experience, or outcome that:

- Is unexpected in terms of nature, severity, or frequency in relation to

- (a) the research risks that are described in the IRB-approved research protocol and informed consent document; Investigator’s Brochure or other study documents, and
- (b) the characteristics of the subject population being studied; **AND**

- Is related or possibly related to participation in the research; **AND**
- Suggests that the research places subjects or others at a *greater risk of harm* (including physical, psychological, economic, or social harm) than was previously known or recognized.

7.2 NCI-IRB AND CLINICAL DIRECTOR REPORTING

7.2.1 NCI-IRB and NCI CD Expedited Reporting of Unanticipated Problems and Deaths

The Protocol PI will report in the NIH Problem Form to the NCI-IRB and NCI Clinical Director:

- All deaths, except deaths due to progressive disease
- All Protocol Deviations
- All Unanticipated Problems
- All non-compliance

Reports must be received within 7 days of PI awareness via iRIS.

7.2.2 NCI-IRB Requirements for PI Reporting at Continuing Review

The protocol PI will report to the NCI-IRB:

1. A summary of all protocol deviations in a tabular format to include the date the deviation occurred, a brief description of the deviation and any corrective action.
2. A summary of any instances of non-compliance
3. A tabular summary of the following adverse events:
 - All Grade 2 **unexpected** events that are possibly, probably or definitely related to the research;
 - All Grade 3 and 4 events that are possibly, probably or definitely related to the research;
 - All Grade 5 events regardless of attribution;
 - All Serious Events regardless of attribution.

NOTE: Grade 1 events are not required to be reported.

7.2.3 NCI-IRB Reporting of IND Safety Reports

Only IND Safety Reports that meet the definition of an unanticipated problem will need to be reported to the NCI IRB.

7.3 IND SPONSOR REPORTING CRITERIA

During the first 30 days after the subject receives investigational agent/intervention, the investigator must immediately report to the sponsor, using the mandatory MedWatch form 3500a, any serious adverse event, whether or not considered drug related, including those listed in the protocol or investigator brochure and must include an assessment of whether there is a reasonable possibility that the drug caused the event. For serious adverse events that occur more than 30 days after the last administration of investigational agent/intervention, only report those that have an attribution of at least possibly related to the agent/intervention.

Required timing for reporting per the above guideline:

- Deaths (except death due to progressive disease) must be reported via email within 24 hours. A complete report must be submitted within one business day.
- Other serious adverse events as well as deaths due to progressive disease must be reported within one business day

Events will be submitted to the Center for Cancer Research (CCR) at: [contact], and to the CCR PI and study coordinator.

7.3.1 Reporting Pregnancy

7.3.1.1 Paternal exposure

Male patients should refrain from fathering a child or donating sperm during the study and for 3 months after the last dose of study treatment. Pregnancy of the patient's partner is not considered to be an AE. However, the outcome of all pregnancies (spontaneous miscarriage, elective termination, ectopic pregnancy, normal birth, or congenital abnormality) occurring from the date of the first dose until 3 months after the last dose should, if possible, be followed up and documented.

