- P. The effects of enzalutamide, PSA-TRICOM or the combination on the developing human fetus are unknown. For this reason, men must agree to use adequate contraception (hormonal or barrier method of birth control; abstinence) prior to study entry and for the duration of study participation. Should a woman become pregnant or suspect she is pregnant while her partner is participating in this study, she should inform her treating physician immediately.

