- *NIH Guidelines for Research Involving Recombinant DNA Molecules (NIH Guidelines). See current version at:*
http://osp.od.nih.gov/sites/default/files/NIH_Guidelines.html

- *Biosafety in Microbiological and Biomedical Laboratories; U. S. Department of Health and Human Services Centers for Disease Control and Prevention and National Institutes of Health. See current edition at: <http://www.cdc.gov/biosafety/publications/index.htm>*

Patient Care Implications and Contraindications

Cover vaccination sites with a sterile dry dressing (e.g., Telfa pad). Once the injection site is healed, no further barrier is necessary. As a precaution, protect injection sites that are exhibiting evidence of weeping, oozing or ulceration with a sterile dry dressing. In these circumstances, instruct patients to avoid direct contact of the injection site with susceptible individuals (e.g.; those who may be immunocompromised by disease or therapy). Instruct patients to avoid fathering a child for at least 4 months following therapy completion with the recombinant vaccine. Instruct patients receiving fowlpox vaccines to avoid direct contact with pet birds for at least 72 hours after vaccination or while there are any visible lesions at the injection site.

Due to the method of manufacturing (virus grown in primary chicken embryo dermal cells), patients with a history of allergy to eggs or egg products should not receive the vaccine.

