Week 5	Physical examination Research Blood, CBC, Acute, Hepatic, Mineral Panels, LDH, CK, Uric Acid, Total Protein, TBNK, PSA, testosterone, PAP, dihydrotestosterone (DHT), sex hormone-binding globulin (SHBG), dehydroepiandrosterone (DHEA), luteinizing hormone (LH), follicle-stimulating hormone (FSH), androstenedione prolactin, estradiol Enzalutamide day 1 month 2 (daily dose of 160 mg)	Physical examination Research Blood, CBC, Acute, Hepatic, Mineral Panels, LDH, CK, Uric Acid, Total Protein, TBNK, PSA, testosterone, PAP, dihydrotestosterone (DHT), sex hormone-binding globulin (SHBG), dehydroepiandrosterone (DHEA), luteinizing hormone (LH), follicle-stimulating hormone (FSH), androstenedione prolactin, estradiol Enzalutamide day 1 month 2 + PSA-TRICOM (Prostvac-F) dose 2
Week 9	Physical examination , CBC, Acute, Hepatic, Mineral Panels, LDH, CK, Uric Acid, Total Protein, TBNK, PSA, testosterone, PAP, dihydrotestosterone (DHT), sex hormone-binding globulin (SHBG), dehydroepiandrosterone (DHEA), luteinizing hormone (LH), follicle-stimulating hormone (FSH), androstenedione	Physical examination , CBC, Acute, Hepatic, Mineral Panels, LDH, CK, Uric Acid, Total Protein, TBNK, PSA, testosterone, PAP, dihydrotestosterone (DHT), sex hormone-binding globulin (SHBG), dehydroepiandrosterone (DHEA), luteinizing hormone (LH), follicle-stimulating hormone (FSH), androstenedione prolactin, estradiol

	Arm A (Enzalutamide only)	Arm B (Enzalutamide + PSA-TRICOM)
	prolactin, estradiol Enzalutamide day 1 month 3 (daily dose of 160 mg)	Enzalutamide day 1 month 3 + PSA-TRICOM (Prostvac-F) dose 3
Week 13	Physical examination , CBC, Acute, Hepatic, Mineral Panels, LDH, CK, Uric Acid, Total Protein, TBNK, PSA, testosterone, PAP, dihydrotestosterone (DHT), sex hormone-binding globulin (SHBG), dehydroepiandrosterone (DHEA), luteinizing hormone (LH), follicle-stimulating hormone (FSH), androstenedione prolactin, estradiol *Apheresis Enzalutamide therapy is discontinued	Physical examination , CBC, Acute, Hepatic, Mineral Panels, LDH, CK, Uric Acid, Total Protein, TBNK, PSA, testosterone, PAP, dihydrotestosterone (DHT), sex hormone-binding globulin (SHBG), dehydroepiandrosterone (DHEA), luteinizing hormone (LH), follicle-stimulating hormone (FSH), androstenedione prolactin, estradiol *Apheresis Enzalutamide therapy is discontinued PSA-TRICOM (Prostvac-F) dose 4

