Week 15	, CBC, Acute, Hepatic, Mineral Panels, LDH, CK, Uric Acid, Total Protein, TBNK, PSA, testosterone, PAP, dihydrotestosterone (DHT), sex hormone-binding globulin (SHBG), dehydroepiandrosterone (DHEA), luteinizing hormone (LH), follicle-stimulating hormone (FSH), androstenedione prolactin, estradiol	, CBC, Acute, Hepatic, Mineral Panels, LDH, CK, Uric Acid, Total Protein, TBNK, PSA, testosterone, PAP, dihydrotestosterone (DHT), sex hormone-binding globulin (SHBG), dehydroepiandrosterone (DHEA), luteinizing hormone (LH), follicle-stimulating hormone (FSH), androstenedione prolactin, estradiol

	Arm A (Enzalutamide only)	Arm B (Enzalutamide + PSA-TRICOM)
Week 17	Physical examination Research Blood, CBC, Acute, Hepatic, Mineral Panels, LDH, CK, Uric Acid, Total Protein, TBNK, PSA, testosterone, PAP, dihydrotestosterone (DHT), sex hormone-binding globulin (SHBG), dehydroepiandrosterone (DHEA), luteinizing hormone (LH), follicle-stimulating hormone (FSH), androstenedione prolactin, estradiol	Physical examination Research Blood, CBC, Acute, Hepatic, Mineral Panels, LDH, CK, Uric Acid, Total Protein, TBNK, PSA, testosterone, PAP, dihydrotestosterone (DHT), sex hormone-binding globulin (SHBG), dehydroepiandrosterone (DHEA), luteinizing hormone (LH), follicle-stimulating hormone (FSH), androstenedione prolactin, estradiol PSA-TRICOM (Prostvac-F) dose 5
Week 21	Physical examination , CBC, Acute, Hepatic, Mineral Panels, LDH, CK, Uric Acid, Total Protein, TBNK, PSA, testosterone, PAP, dihydrotestosterone (DHT), sex hormone-binding globulin (SHBG), dehydroepiandrosterone (DHEA), luteinizing hormone (LH), follicle-stimulating hormone (FSH), androstenedione prolactin, estradiol	Physical examination , CBC, Acute, Hepatic, Mineral Panels, LDH, CK, Uric Acid, Total Protein, TBNK, PSA, testosterone, PAP dihydrotestosterone (DHT), sex hormone-binding globulin (SHBG), dehydroepiandrosterone (DHEA), luteinizing hormone (LH), follicle-stimulating hormone (FSH), androstenedione prolactin, estradiol PSA-TRICOM (Prostvac-F) dose 6

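### For Arm B patients whose last study dose is fowlpox vaccine, the 3-month tail in section 7.3.1.1 is one month shorter than the vaccine sections require

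*Combined protocol and SAP*

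**What the plan says.** Section 7.3.1.1 (Paternal exposure) has two tails of 3 months, with no separate rule for vaccine recipients:

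- Restriction: "Male patients should refrain from fathering a child or donating sperm during the study and for 3 months after the last dose" of study treatment.
- Outcome request: pregnancies "occurring from the date of the first dose until 3 months after the last dose should, if possible, be followed up and documented".

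Section 11.1.6 (fowlpox vaccine) says patients are to be told to "avoid fathering a child for at least 4 months following therapy completion with the recombinant vaccine". Section 11.2.6 gives vaccinia recipients the same minimum of 4 months.

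The Arm B schedule in Appendix C shows "Enzalutamide therapy is discontinued" at week 13 and "PSA-TRICOM (Prostvac-F) dose 6" at week 21. Section 3.2 confirms week 21 as the last vaccination.

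Inclusion criterion P (section 2.1.1) states: "The effects of enzalutamide, PSA-TRICOM or the combination on the developing human fetus are unknown". It requires contraception "prior to study entry and for the duration of study participation", with no period after participation ends. If a partner becomes pregnant "while her partner is participating in this study, she should inform her treating physician immediately". It does not ask for the outcome to be recorded.

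**The concern.** The protocol gives two different end dates for the same precaution. Section 7.3.1.1 counts from the last dose of any study treatment. In Arm B that dose is normally a vaccine dose, and the vaccine section asks for a longer period.

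Two things follow. First, a pregnancy in the fourth month after the last vaccine lies inside the protocol's own vaccine precaution but outside the period for which outcomes are requested. Second, a patient who leaves the study soon after week 21 has 3 months in one section, at least 4 months in another, and no post-study period in criterion P. What is at stake is partner safety information and consistent advice, not the trial's comparison of PSA growth.

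**Working it through.** The plan states no figure to reproduce, so this is calendar arithmetic on the schedule.

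**Inputs**
- Outcome window and restriction tail: 3 months after the last dose (7.3.1.1).
- Vaccine restriction: at least 4 months after completing vaccine (11.1.6).
- Last fowlpox dose: week 21 (3.2, Appendix C). First enzalutamide course ends: week 13 (Appendix C).
- Second enzalutamide course: only after at least 7 months on study (Précis). It lasts 12 weeks.
- Month length (assumption): 365.25 / 12 / 7 = 4.348 weeks, so 3 months = 13.04 weeks and 4 months = 17.39 weeks.

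**Formulas**
- End of the 7.3.1.1 tail = max(last vaccine week, last enzalutamide week) + 13.04.
- End of the 11.1.6 restriction = last fowlpox week + 17.39.

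**Results, no second course, enzalutamide to week 13**

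| Last fowlpox dose | 7.3.1.1 tail ends | 11.1.6 restriction ends | Gap (weeks) |
|---|---|---|---|
| Week 21 | 34.04 | 38.39 | 4.35 |
| Week 17 | 30.04 | 34.39 | 4.35 |
| Week 13 | 26.04 | 30.39 | 4.35 |
| Week 9 | 26.04 | 26.39 | 0.35 |
| Week 5 | 26.04 | 22.39 | none |

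**Month length, week-21 case.** With 28-day months the dates are weeks 33.0 and 37.0, a gap of 4.0. With 31-day months they are 34.29 and 38.71, a gap of 4.43 before rounding. In every case the gap is 4 months minus 3 months. Because 11.1.6 says at least 4 months, it is a minimum.

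**Second course.** The earliest start is 7 × 4.348 = 30.44 weeks after enrolment. Adding 12 weeks of drug and 13.04 weeks of tail gives 55.48 weeks. With 28-day months it is 28 + 12 + 12 = 52 weeks. Both are later than the vaccine restriction, so there is no gap.

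**Vaccinia, read for its own dose.** 1 + 17.39 = week 18.39, which is before week 26.04. It creates no gap by itself, so the point rests on fowlpox.

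**Restriction for early leavers, last vaccine week 21.** Shortfall = 38.39 − max(off-study week, 34.04), not below 0. Off study by week 34.04: 4.35 weeks. Off study at week 36: 2.39 weeks. On study at week 38.39 or later: 0.

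**Patients exposed.** Arm B only: 17 planned, or 38 / 2 = 19 if the accrual ceiling is reached at 1:1.

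**The case against.** The strongest reply is that outcome follow-up and the fathering restriction need not have the same length, and the protocol never says they should. Section 7.3.1.1 itself separates them in both arms. The restriction runs throughout the study, but outcome follow-up is tied to dosing. An Arm A patient without a second course can be restricted to week 52 while the outcome window closes at 13 + 13.04 = week 26.04, about 26 weeks sooner. This stands. A reader might infer that outcomes should be requested for the whole on-study restriction, which in Arm B would add 52 − 34.04 = about 18 weeks. The documents do not support that. They support only correcting the length of the post-dose tail.

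It is also true that on-study patients are already restricted to week 52 by 7.3.1.1 and criterion P. For those who leave early, the two instructions are compatible, since observing 4 months satisfies 3.

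Other provisions might be thought to catch a fourth-month pregnancy, but none visible here clearly does:
- Section 7.3.1.1 says a partner's pregnancy is not an adverse event, and 7.1.1 defines adverse events in the research subject.
- Section 7.1.5 lists birth defects among serious outcomes. More than 30 days after dosing, however, section 7.3 asks only for serious events that are at least possibly related, so it would not collect pregnancy outcomes in general.
- Section 3.7 offers Arm B patients a separate long-term follow-up protocol but does not mention pregnancy outcomes.

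The request is softened by a proviso about feasibility. That qualifies the effort, not the date range.

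**Conclusion.** The inconsistency is real and minor. For an Arm B patient whose last study dose is fowlpox vaccine, the 7.3.1.1 tail is one month short, about 4 weeks. For outcome follow-up this holds on or off study. For the restriction it matters only to patients who leave before 4 months after their last vaccine.

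Three stronger readings are not supported:
- **That harm is likely in that month.** Section 11.1 says fowlpox virus does not replicate outside birds, and by week 34 the single vaccinia dose is 33 weeks old. The ground for acting is only that criterion P calls fetal effects unknown and the protocol set its own 4-month precaution.
- **That patients will be wrongly counselled.** Advice may come from the consent form and the Appendix B instruction sheet, which were not available for this review.
- **That the trial's results are affected.** The endpoint, power, randomisation and analysis are untouched.

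The result assumes no second enzalutamide course, a last fowlpox dose at week 13 or later, and completion of vaccine counted from the last injection. The documents give no rate for early exit, second courses or partner pregnancy, so no expected number of cases is offered.

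**What to change.** In section 7.3.1.1, for Arm B, replace both 3-month tails with: *at least 4 months after the last vaccine dose or 3 months after the last enzalutamide dose, whichever is later*. Keep the existing restriction during the study. Add the same tail to criterion P, and check that the consent form and Appendix B agree. Do not tie the outcome request to the whole on-study restriction period.

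The cost is amendment wording in two sections, plus consent and instruction-sheet wording if those disagree. No visits or procedures are added. After a week-21 last vaccine without a second course, the outcome window moves from about week 34.0 to about week 38.4, and the gap closes.
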